There have been no large-scale controlled studies in sub-saharan Africa evaluating the effectiveness of a BNI for alcohol. Given Sub-Saharan African patients have limited care-seeking behaviors and limited harmful alcohol use treatment options with a growing burden of alcohol, the unique opportunity to screen and intervene upon high proportions of high-risk alcohol behavior patients during a "teachable moment" in the ED in Tanzania, warrants an evaluation of an alcohol BNI effectiveness.

Statement of the Problem:

Currently, we know that the injury patients who present to the KCMC Casualty Department have a high prevalence of harmful and hazardous drinking behaviors which might be amenable to intervention. While we have an intervention that has shown to be effective in high income

Version 9Feb2021 Page **6** of **21**

settings, we have not had an intervention which is translated and validated for the Tanzanian environment to address high risk alcohol use.

Rationale:

Given this need and potential intervention, this project will gather information in order to define the stigma, customs and cultures around alcohol use and will prepare and test an intervention for alcohol use in Tanzania.

Broad Objectives:

Broad Objective 1: Describe the current perspectives on alcohol use

Broad Objectives 2: Develop a culturally appropriate intervention for alcohol use.

Broad Objectives 3: Conduct a pilot trial of the intervention.

Specific Objectives:

Specific Objective 1: Define patient's current perspectives on alcohol use.

Specific Objective 2: Define families' and the public's current perspectives on alcohol use.

Specific Objective 3: Define healthcare providers' current perspectives on alcohol use.

Specific Objective 4: Translate, and iteratively improve a culturally-appropriate nurse-delivered brief negotiational interview (BNI) utilizing motivational interviewing, to be delivered in the KCMC Emergency Department.

Specific Objective 5: Validate measures which will be utilized to evaluate the intervention.

Specific Objective 6: Conduct a pilot trial of the intervention in order to validate study procedures.

Specific Objective 7: Conduct a pilot trial in order to evaluate the intervention acceptability.

Specific Objective 8: Conduct a pilot trial in order to evaluate the enrollment and retention rates.

Methods:

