Sample Size Calculation: For the injury patient surveys, sample size will be calculated to determine the proportion of harmful alcohol use based upon the AUDIT tool, (see Appendix) which will be an inclusion criterion for Aim 3. A sample size of 323 injury patients will allow us to estimate our anticipated AUDIT positive (>8) proportion of patients anticipated at 30% to within +/- 5% (95% confidence interval). However, given the patient volume, we likely will recruit additional patients. Surveys will be conducted for 16-24 weeks. Conservative estimates of patients who could be enrolled are seen in Table 4.

For family member surveys, our goal is to get 1 family member per patient yet recognizing that approximately 30% of patients may have no accompanying family members. Thus, our sample of family members is estimated to be at least 226 family members. As for the healthcare practitioners, there are 50 professionals affiliated or connected to the emergency department, considering a 10% loss due to rotation or annual leave, our aim is to get at least 45 practitioners included in the survey.

Data Collection: Surveys will be verbally administered to patients and families due to variable literacy rates. Surveys will be self-administered by healthcare providers in the standard medical language of English or Swahili. Focus groups will be conducted, once weekly until saturation, and will be audiotaped, transcribed, and translated. They will focus on the prevalence of harmful and hazardous alcohol use, the cultural acceptance of alcohol, moderators of alcohol use, and current perspectives on the feasibility and potential impact of a brief intervention.

Data Analysis: Survey results will be analyzed through a range of descriptive and analytical techniques. Pertinent outcome variables are expected to be dichotomous. (e.g., hazardous drinking, care-seeking behavior, injury outcomes). Then, for all three surveys (patients, family and healthcare providers) basic descriptive associations of sociodemographic characteristics

Version 9Feb2021 Page **11** of **21**

and binary outcomes (when applicable) will be examined using chi-square tests, and logistic regression analyses. Our goal is to determine patterns of associations between sociodemographic variables, harmful alcohol use and related injury, and attitudes and practices towards alcohol use. Open-ended survey items and focus group data will be analyzed into response categories using nVivo. Latent Semantic

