Aim 3: Conduct a pilot trial of the intervention. Feasibility of 1) study procedures, 2) patient acceptability of the intervention and trial, and 3) patient enrollment/retention will be tested in a pilot RCT.

Introduction and Rationale: To test the intervention's effectiveness for at risk and harmful alcohol use reduction, an adequately powered pragmatic clinical trial with maximum external validity is the next step to evaluate this intervention.⁴⁴ To prepare for this clinical trial, a feasibility trial should be conducted prior to a large scale trial, as the most essential pre-requisite of a trial enhancing the likelihood of success of a RCT.⁴⁵

Research Design: This will be a pilot 4, 8 block randomized feasibility and acceptability trial.

Participants and Recruitment: We will prospectively enroll (n=75, across 4 arms) patients who present to the KCMC ED for care of acute injuries and meet inclusion and exclusion criteria: >18 years of age, be clinically sober at the time of enrollment, have capacity to give informed consent, converse in the local language Swahili or in English, and have either 1) reported ingesting alcohol in the 6 hours prior to injury, 2) have a positive breathalyzer test, or 3) have an Alcohol Use Disorder Identification Test with a score of ≥8. Our trained research nurses will

Version 9Feb2021 Page **15** of **21**

describe the intervention as a health assessment, and eligible interested participants will be enrolled, provide informed consent and a randomization packet chosen. They will then administer patient demographic, injury, alcohol use surveys and the intervention if appropriate all lasting less than 45 minutes.

[figure not shown]

Figure 1: Pragmatic Randomized Adaptive Clinical Trial Design

Follow up Procedures: All groups will provide two phone numbers where they can be reached in order to facilitate follow up. All participants will be contacted at 6 weeks, 3 months, and 6-months post-discharge for follow-up survey administration. Surveys are expected to be less

than 20 minutes. All patients will be contacted by text message at the conclusion of the study to inform them about availability of the results of the study.

Study	Protocol Deviation	Intervention	Survey	
Procedures	Event Analysis	Fidelity: BNI	Time	
		Assessment		
		Observations		
Acceptability	Questionnaires			
Recruitment &	Enrollment Rate	Enrollment/Retention Failure		
Retention	Retention Rate	Event Analysis		
Table 7: Feasibility Trial Outcomes				

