Version 9Feb2021 Page **16** of **21**

We will conduct a feasibility assessment subjectively through self-assessments as well as objectively through Event Analyses, understanding causes of deviations from protocol, Intervention Observations and Questionnaires.

Study Procedures: To evaluate the study procedures, we will evaluate any protocol deviation events, and compare length of survey times. We will also perform assessments of intervention fidelity through real-time observations of BNI administration using the BNI Assessment Scale similar to the procedure in Aim 2.

Intervention and Trial Acceptability: We will assess acceptability of participation in trial and intervention through questions after the final follow up timepoint for both the research team as well as participants. Assessment about the length of surveys, method of follow-up, number of follow-up calls,

Enrollment and Retention: The primary outcome measure will be recruitment and retention rates. Secondarily, we will qualitatively assess the inclusion and exclusion criteria, reasons for non-enrollment or non-retention, to the extent possible. Finally, follow-up questions about remuneration procedures in order to improve enrollment or retention will be administered after enrollment or on the completion of follow up.

Sample Size: In total, 75 participants will be recruited (randomized across 4 arms). This sample size is based on what is needed to evaluate study process fidelity, intervention acceptability, and recruitment and retention assessment. This sample size will allow us to estimate our desired minimal recruitment rate of 30% to within +/- 11% (95% confidence interval) and to estimate our desired retention rate of 80% within +/- 10%. Further, it is anticipated to provide sufficient opportunity to uncover significant acceptability concerns. We are not proposing an adequately powered study nor an effect size calculation as pilot studies may not accurately represent effect sizes of the main study. ⁴⁶

Ethical Considerations Subject Recruitment and Compensation

For objective 1, all healthcare workers at KCMC Casualty Department will be offered enrollment in the study. The only cost to participants is the time spent performing the survey. The participants will not be compensated for their time for this study. For objective 2, a snowball method of sampling key informants will be utilized to recruit subjects for enrollment in the key

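### The ±11-point precision for the 30% recruitment rate treats the 75 recruits as the denominator; with 75 recruited it is about ±6 points, and the denominator is never defined

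*Combined protocol and SAP*

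**What the plan says.** All references are to the combined protocol and SAP.

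- Aim 3, Participants and Recruitment: "We will prospectively enroll (n=75, across 4 arms) patients".
- Aim 3, Sample Size: "In total, 75 participants will be recruited (randomized across 4 arms".
- The same paragraph, on recruitment: "This sample size will allow us to estimate our desired minimal recruitment rate of 30% to within +/- 11% (95% confidence interval".
- The same sentence, on retention: the size also serves "to estimate our desired retention rate of 80% within +/- 10" percentage points.
- Aim 3, Enrollment and Retention: "The primary outcome measure will be recruitment and retention rates".
- Specific Objective 8: "Conduct a pilot trial in order to evaluate the enrollment and retention rates".

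Table 7 lists an enrollment rate and an event analysis of enrollment and retention failures. It does not define the rate. For Aim 3 the plan gives no number to be screened, found eligible or approached, and no interval method.

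**The concern.** A recruitment rate is the number recruited divided by the number who could have been recruited. The plan sets the first of these at 75 and leaves the second open. A precision statement for the rate needs the second number, so ±11 points cannot be derived from the text as it stands. The figure looks as if the 75 were carried over from the retention calculation, where they are the correct denominator.

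Two things are at stake. The stated precision of a primary outcome should match the design. And with no named denominator, the same 75 recruits can give different rates, above or below the desired 30% minimum, depending on whom one counts. The pilot is meant to inform a larger trial, so that ambiguity would carry into its planning.

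**Working it through.** **Inputs.** Recruited: 75 (Aim 3, Participants and Recruitment; Sample Size). Recruitment rate 30%, stated half-width 11 points, 95% interval, taken as two-sided (Sample Size). Retention rate 80%, stated half-width 10 points (same sentence).

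**Formulas.** Wald half-width = 1.96 × √(p(1 − p)/n). The continuity-corrected version adds 1/(2n). The exact interval is Clopper-Pearson, and its half-width is half its length.

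**1. Reproducing the plan's figure, with 75 as the denominator.**

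- Wald: 1.96 × √(0.30 × 0.70/75) = 10.4 points.
- Continuity-corrected: 10.37 + 100/(2 × 75) = 11.0 points.
- Exact: 10.8 points for 22/75, 10.9 for 23/75.

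So ±11 can be reproduced, but only with 75 in the denominator. The number recruited would then be 0.30 × 75 = 22.5, not 75.

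**2. With 75 as the number recruited, as the text says.**

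- Denominator: 75/0.30 = 250.
- Wald: 1.96 × √(0.30 × 0.70/250) = 5.7 points.
- Continuity-corrected: 5.68 + 100/(2 × 250) = 5.9 points.
- Exact for 75/250: 24.4% to 36.1%, half-width about 5.9 points.
- Treating 75 recruits as a fixed stopping count (inverse sampling): 1.96 × 0.30 × √(0.70/75) = 5.7 points.

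All of these round to 6 points.

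**3. Other recruitment rates (assumed), still with 75 recruits.**

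| Rate | Denominator | Wald half-width (points) |
|---|---|---|
| 20% | 375 | 4.0 |
| 30% | 250 | 5.7 |
| 40% | about 188 | 7.0 |
| 50% | 150 | 8.0 |

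**4. Can any denominator give ±11?** With 75 recruits, n = 75/p, so the Wald half-width is 1.96 × √(p²(1 − p)/75). This is largest at p = 2/3, where n is about 113, and equals 8.7 points. Over denominators from 76 to 999 the maximum is 9.1 points for the exact interval and 9.2 with the continuity correction. The answer is no, whichever of these methods was used.

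**5. Working back from ±11.** At 30%, the Wald formula needs n = 1.96² × 0.21/0.11² ≈ 67, that is, about 20 recruits.

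**6. Retention check, 80% of 75.** Wald: 1.96 × √(0.80 × 0.20/75) = 9.1 points. Continuity-corrected: 9.7. Exact for 60/75: 9.6. The stated ±10 points is sound for the 75 pooled across arms.

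**The case against.** **The statement is still true as an upper bound.** An estimate good to 6 points is also good to 11. But the sentence is offered as the precision that this sample size provides. A reader takes it as the expected interval width, and on that reading it is wrong.

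**The arithmetic is not at fault.** This is fair. The number 11 can be reproduced; the fault is in which quantity was used as n. Even that is an inference, because no method is given. The Wald formula, which reproduces the Aim 1 figure (323 patients, 30%, ±5 points: 1.96 × √(0.21/323) = 5.0), gives 10.4 at n = 75, so reaching 11 needs an exact interval, a continuity correction or rounding up. The finding does not depend on how the 11 arose, since step 4 shows that it cannot arise from 75 recruits.

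**Perhaps 75 means 75 approached.** Both Aim 3 passages describe the 75 as enrolled or recruited across four arms. If approached was meant, both need correcting, and only 22 or 23 people would be randomised.

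**Little depends on it.** This stands. The plan disclaims a powered comparison, no go/no-go rule uses the half-width, and the sample size also rests on process fidelity, acceptability and retention.

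**The denominator is partly covered.** The plan enrols eligible, interested patients, has the failure event analysis in Table 7, and intends to record reasons for non-enrollment as far as it can. That implies some recording of patients who do not enrol, but it neither names a denominator nor promises a complete count.

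**Conclusion.** The concern holds and is minor. With 75 recruited at a 30% rate, the 95% half-width is 5.7 to 5.9 points on about 250 people, against the stated 11. Near 30% the precision is about twice as good as claimed (11/5.7 ≈ 1.9); at 40% and 50% the ratio falls to about 1.6 (11/7.0) and 1.4 (11/8.0). The error is in the safe direction: 75 does not need to rise, and the retention precision is unaffected.

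This rests on reading 75 as the number recruited, as both Aim 3 passages say, and on a two-sided 95% interval for a single proportion. The undefined denominator is the more useful part in practice, because without it this component of the primary outcome has no single value.

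**What to change.** In the Aim 3 Sample Size paragraph:

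1. Name the denominator of the recruitment rate, for example eligible patients approached. The choice is the sponsor's. Use the same definition for the enrollment rate in Table 7.
2. Replace the ±11% statement with wording such as: *At a 30% recruitment rate, recruiting 75 participants implies about 250 patients in the denominator and estimates the rate to within about ±6 percentage points (95% CI).* Name the interval method.
3. Keep ±10% for retention, and say that it refers to the 75 randomised participants pooled across arms.
4. Log every patient who falls in the chosen denominator, so that the rate can be computed.

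The cost is a wording change. It adds no participants and alters neither design nor analysis. The log fits the enrollment rate and the enrollment-failure event analysis already planned in Table 7.
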